2.1 Primary objective

To verify the superiority of duloxetine over placebo, using change from baseline in CDRS-R total score as the index.

2.2 Secondary objectives

- To evaluate the efficacy of duloxetine compared with placebo on the basis of the following indices:
 - 30% response rate: Proportion of subjects showing CDRS-R total score decreases of 30% or more from baseline.
 - 50% response rate: Proportion of subjects showing CDRS-R total score decreases of 50% or more from baseline.
 - Remission rate: Proportion of subjects with CDRS-R total scores of 28 or lower
 - Change from baseline in CDRS-R subscales and item 13 (suicidal ideation)
 - Change from baseline in CGI-S score
- To evaluate the safety of duloxetine, with occurrence or non-occurrence and frequency of adverse events and adverse drug reactions as indices.

3. Study plan

3.1 Study design

[figure not shown]
This study is to be a multicenter, randomized, placebo-controlled, double-blind, parallel-group, comparative study with children and adolescent patients with depressive disorder, with the target number of subjects being 148. It will consist of the following four periods: Screening period (1-3 weeks), treatment period (6 weeks), Tapering period (1 week), Follow-up period (1 week), (total: up to 11 weeks). During the treatment and tapering periods (total: 7 weeks), duloxetine or placebo will be administered orally, once daily after breakfast. Subjects who transfer to the extended long-term treatment study [study no.: 1702A3632 (NCT03395353)] will transfer to the extended study after completion of the tapering period.

- Screening period: After obtaining informed consent, eligibility has to be confirmed at Visit 1, and subjects for whom this is confirmed will then be pre-registered. In addition, the first session of psycho-education will be provided, and the subjects' conditions will be assessed.
- Treatment period: Eligibility will be confirmed again at Visit 2, and subjects for whom this is confirmed will then be registered. The subjects will then be allocated randomly, with double-blinding, to the duloxetine and placebo groups, in a 1:1 ratio, and will be orally administered duloxetine or placebo once daily after breakfast, for 6 weeks. With the duloxetine group, administration will be initiated at 20 mg/day, and increased to 40 mg/day at Visit 3, 1 week later. From Visit 4, 1 week after Visit 3, if the CGI-S score is 3 or higher, and there are no concerns about safety, the dose will be increased to 60 mg/day. In addition, from Visit 5, after the dose has been temporarily increased to 60 mg/day, if there are safety-related problems, it can be reduced again to 40 mg/day. If the CGI-S score is ≥ 3 , and there are no safety-related problems, after confirming the subject's clinical condition and safety, the dose can be increased again. When the dose is to be increased from 20 to 40 mg/day, or from 40 to 60 mg/day for the first time, the pre-increase dose must be administered for at least 7 days. Visit 6 is a visit that can be made to the hospital in connection with dose increase, decrease, etc.
- Tapering period: In order to minimize the occurrence of adverse events due to discontinuation of administration, a 1-week tapering period is set for subjects who complete the treatment period, or who withdraw from it during the second week or later, and during this time duloxetine or placebo will be administered orally, once daily after breakfast, with double-blinding. If the duloxetine dose at discontinuation or completion of the treatment period is 60 mg/day, 40 mg/day will be administered for the first 3 days of the 1-week tapering period, and 20 mg/day will be administered for the remaining 4 days. On the other hand, if the dose at discontinuation or completion is 40 mg/day, 20 mg/day will be administered for the entire week (for details about the tapering method at discontinuation of the treatment period, refer to Section 5.2).
- Follow-up period: No study drugs will be administered during the 1-week follow-up period. This period is set to enable evaluation of any adverse events during the week after completion of study drug administration, irrespective of whether or not the dose was tapered. If administration is discontinued during the treatment period, and there is then no administration during the tapering

period, a 1-week run-out period will be set after administration discontinuation.

The study design is shown in Fig. 3-1. The study schedule is shown in Appendix 1.

Fig. 3-1. Schematic diagram of study schedule

a Visit 6 is a visit that can be made to the hospital in connection with dose increase, decrease, etc.

3.2 Rationale for setting the study design

(1) Rationale for setting the screening period

This period is set for the following reasons:

- In order to select appropriate patients for study participation, on the basis of the results of observation and tests before initial administration.
- In order to eliminate carry-over effects if contraindicated drugs and/or therapies were being used at the time of joining the study.
- So that diagnoses are made twice, before the pre-registration and registration, enabling selection of the most appropriate subjects.

(2) Rationale for setting placebo as the control drug

A double-blind, parallel-group, comparative study is the standard design for evaluation of the efficacy of antidepressants in acute-phase depression. No drugs are currently indicated for pediatric depression in Japan, so placebo is set as the control.

(3) Rationale for setting the doses (the same as for adults with depression or depressive state in Japan)

Three overseas studies, the HMFN, HMCK and HMCL studies, have been performed with children and adolescent major depressive disorder patients, diagnosed in accordance with DSM-IV and DSM-IV-TR, and the plasma duloxetine concentrations measured in these studies were compared with those in overseas adult patients. The ratios in the median plasma duloxetine concentrations in children subjects (7 to 11 years old) and adolescent subjects (12 to 17 years old) compared with the dose-corrected plasma duloxetine concentration in adult patients were 0.829 and 0.686, respectively. Although the values were thus somewhat lower in children and adolescent patients, the ratios were not great enough to necessitate dose adjustment. In addition, plasma duloxetine concentration shows widevariation in children, adolescent and

adult patients, and no differences between these three groups were found in the distribution range of dose-corrected plasma concentration measurements. Furthermore, on the basis of a steady-state plasma concentration simulation, it has been predicted that similar plasma concentration time-courses will be shown with pediatric and adult patients when the same doses are administered. For these reasons, it is considered that administration of the same dose to children and adolescent patients as to adult patients will result in approximately the same level of exposure.

The pharmacokinetic parameters for duloxetine, that is, the maximum plasma concentration (C_{max}) and the area under the curve for plasma concentration against time (AUC), have been compared between Japanese and non-Japanese (Caucasian and black) healthy adults, and no statistically significant ethnic differences have been found. It has thus been confirmed that, with the same duloxetine dose, the plasma concentration is approximately the same in overseas adults and children, and in overseas and Japanese adults, and the dose in this study has thus been set the same as that used in Japan for adult depression and depressive state patients.

(4) Rationale for setting administration period (6-week treatment period)

The administration period set for clinical studies on antidepressants is 6 to 8 weeks in the Japanese guidelines (1), and at least 4 and approximately 6 weeks in the European Medicines Agency guidelines (14). The study drug administration period set for the present study, 6 weeks, is within the range set by the Japanese guidelines, and the administration period after reaching the maintenance dose, 4 to 5 weeks, complies with the European Medicines Agency guidelines.

In practice, even the Phase-3 duloxetine verification study results, which were included in the Japanese approval application data package for adult depression and depressive state patients, verified superiority over the placebo group with a 6-week administration period.

In addition, in the HMCL study, which was the one of the overseas Phase-3 studies with which the results suggested efficacy, the adjusted mean CDRS-R change in patients aged ≥ 9 to < 18 at the time of obtaining informed consent, and ≥ 7 at initial onset of depression, was consistent from 1 week after initiation of administration, and was greater with duloxetine than with placebo. Furthermore, no major change differences between duloxetine 60mg and placebo were found at any time from 1 week after administration initiation. For the above reasons, the administration duration has been set at 6 weeks.

(5) Rationale for setting the tapering period

The duloxetine package insert states that, if administration is to be discontinued, in order to avoid withdrawal symptoms, administration should be tapered off rather than discontinued suddenly. Therefore, taking subjects' safety into consideration, tapering of administration has been set after completion or discontinuation of the treatment period.

3.3 Study period:

3.3.1 Study period for each subject

Up to a total of 11 weeks, consisting of a 1- to 3-week screening period, a 6-week treatment period, a 1-week tapering period, and a 1-week follow-up period.

3.3.2 Scheduled period of entire study

October 2017 to February 2020

4. Inclusion of subjects and discontinuation of study

4.1 Study subjects

Children and adolescent patients with depressive disorder who meet the following inclusion criteria and do not meet any of the exclusion criteria will be included in this study.

4.2 Inclusion criteria

Subjects must meet all the following criteria:

- 1) At Visit 1, they have been diagnosed as having depression or persistent depressive disorder, as defined in DSM-5, and fully meet the criteria for depressive episodes. MINI-KID (version 7.0.2) is used for diagnosis of depression.
- 2) They must be aged ≥ 9 to < 18 at the time of obtaining consent and assent, and must have been ≥ 7 at the initial onset of depression. They can be of either sex, and be either hospitalized or out-patients, but patients for whom the principal investigator or sub-investigator judges change in hospitalization status to be necessary between Visits 1 and 8 are excluded.
- 3) At Visits 1 and 2, the CDRS-R total score is ≥ 40 , and the CGI-S score is ≥ 4 .
- 4) By Visit 1, freely given, written, informed consent for participation in the study has been obtained from the patient's legal representative. In addition, in the case of patients aged ≥ 13 , written, informed assent has also been obtained from the patient him/herself. In the case of patients aged ≥ 9 to < 13 , written, informed assent is obtained from the patient him/herself, if possible.
- 5) In the case of post-menarchic females, a pregnancy test must give a negative result at Visit 1. In addition, the patient must consent to use one of the below contraceptive methods from Visit 1 until 1 month after the final administration. However, this requirement does not apply to females for whom it can be confirmed in writing that 6 weeks or more has passed since bilateral ovariectomy.
Estrogen- and progesterone-containing, combined-hormonal contraceptive agents with ovulation-suppressing effects (administered orally, intravaginally, subcutaneously, etc.), progesterone-containing hormonal contraceptive agents (administered orally, intravenously, by implantation, etc.), intrauterine device, intrauterine system, bilateral tubal ligation, male partner's vasectomy, or sexual abstinence.
- 6) The principal investigator or sub-investigator judges that the patient's legal representative can ensure that the patient him/herself will comply with all the hospital visits, tests, and other procedures stipulated in this protocol. In addition, the principal investigator or sub-investigator judges that the patient him/herself will be able to comply with all the hospital visits, tests, and other procedures stipulated in this protocol.
- 7) The principal investigator or sub-investigator judges that the patient's legal representative has sufficient comprehension ability and cognitive ability to communicate as appropriate with the principal investigator or sub-investigator, and other persons involved with the study. In addition, the principal investigator or sub-investigator confirms that the subject him/herself has a cognitive level appropriate to his/her age, and judges that he/she has sufficient comprehension ability and

cognitive ability to communicate as appropriate with the principal investigator or sub-investigator, and other persons involved with the study.

- 8) The patient can swallow the capsules without opening, crushing, dissolving, or breaking them. In addition, he/she can take up to three capsules per day.

4.3 Exclusion criteria

Patients who meet one or more of the following criteria are excluded:

- 1) Between Visits 1 and 2, the CDRS-R total score improves by 30% or more.
- 2) Judged by the principal investigator or sub-investigator to have complications diagnosed as belonging to one or more of the following categories in DSM-5, or to have a history of such disorders:
 - Neurodevelopmental disorders
 - Schizophrenia-spectrum disorder or other psychotic disorders
 - Bipolar or related disorders
 - Emotional trauma or stress disorders
 - Disruptive, impulse-control, and conduct disorders
- 3) Judged by the principal investigator or sub-investigator to have complications diagnosed as belonging to one or more of the following categories in the DSM-5:
 - Obsessive-compulsive disorder or related disorders
 - Anorexia nervosa, bulimia nervosa, or binge-eating disorders
 - Sleep-wake disorders
 - Neurocognitive disorders
 - Disruptive mood dysregulation disorders
- 4) Judged by the principal investigator or sub-investigator to have a personality disorder.
- 5) Treatment with two or more antidepressants has previously been tried, and, despite administration of the optimal clinical dose for the depressive episode for 4 weeks or more, no response was seen. Alternatively, the depressive episodes were previously treated with duloxetine, and no response was seen.
- 6) Depressive episodes currently being treated with duloxetine.
- 7) The principal investigator or sub-investigator judges that systematic psychotherapy must be initiated between Visits 1 and 9.
- 8) One or more of the patient's parents and/or siblings has been diagnosed as having bipolar disorder.
- 9) A history of epileptic or other convulsive attacks. However, patients with a history of febrile convulsions can be enrolled.
- 10) Administered electroconvulsive therapy within 1 year before Visit 1.
- 11) Used contraindicated drugs or therapies between Visit 1 (pre-registration) and Visit 2 (registration).
- 12) Uncontrolled diabetes or collagen disease.
- 13) Hormonal therapy initiated, changed or discontinued within 3 months before Visit 1. Patients with

thyroid dysfunction are excluded, unless they (i) have undergone thyroid hormone supplementation for at least 3 months as of Visit 1; (ii) show medically appropriate concentrations of thyroid hormones (TSH, FT3 and FT4); and (iii) have attained a clinically normal state of thyroid function.

- 14) Currently have or have a history of malignant tumors/cancer.
- 15) Suicidal ideation and/or suicidal attempt within 1 year before Visit 1; and/or, at Visits 1 and 2, answer "Yes" on C-SSRS questions 4 and/or 5 about suicidal ideation, and/or any of the questions about suicidal behaviors (except for questions about non-suicidal self-injurious behavior).
- 16) Body weight below 20 kg at Visit 2.
- 17) Serious^{*1} or medically unstable disease^{*2} (cardiovascular disease, hepatic disease, respiratory disease, hematologic disease, endocrine disease, peripheral vascular disorder, neuropsychiatric disease, renal disease), or clinically problematic abnormal laboratory test results or abnormal ECG findings^{*3}.

*1: Grade 3 in "Concerning classification criteria for seriousness of adverse drug reactions to pharmaceutical products, etc." (Drug Safety Notification no. 80; June 29, 1992).

*2: Judged by the principal investigator or sub-investigator to have the potential to disrupt study participation, or to necessitate hospitalization during the study period.

*3: Judged by the principal investigator or sub-investigator to suggest serious medical issues, or to necessitate aggressive therapy.

- 18) Meeting one or more of the following criteria:
 - At Visit 1, 100 U/L or higher ALT or AST, or 1.6 mg/dL or higher total bilirubin.
 - Serum creatinine level of 2.0 mg/dL or higher at Visit 1, severe renal impairment, history of renal transplantation, and/or currently undergoing renal dialysis.
- 19) Glaucoma, elevated intraocular pressure, and/or prostatic hypertrophy or other types of dysuria.
- 20) Depression or depressive state due to organic brain disorder.
- 21) Hemorrhagic tendency or hemorrhagic diathesis.
- 22) Treatment with monoamine oxidase (MAO) inhibitor within 14 days before Visit 2, and/or potential for MAO inhibitor treatment during the study period or within 5 days after completion of study drug administration
- 23) Hypersensitivity to duloxetine or active ingredients of duloxetine.
- 24) Allergic to two or more drugs, or a history of serious allergic reaction to one or more drugs.
- 25) Judged by the principal investigator or sub-investigator to have his/her condition complicated by substance-related and/or addictive disorders, as defined in DSM-5, or to have a history of such disorders. However, patients with caffeine-related disorder can enroll.
- 26) One or more substances of abuse (phencyclidine, benzodiazepines, cocaine-type drugs, stimulants, cannabis, opioids, barbiturates, tricyclic antidepressants, etc.) detected by urinary drug screening at Visit 2.
- 27) Intention to travel overseas between Visit 1 (pre-registration) and Visit 10 (or Visit 9 in the case of transfer to the extended long-term treatment study).

28) Pregnant* or possibly pregnant, breastfeeding, hoping to become pregnant during the study period, or recently given birth.

* Pregnancy: At Visit 1, pregnancy tests (blood or urine human chorionic gonadotropin) are performed with all post-menarchic females.

29) Previously administered the study drug during participation in this study, or during participation in a different clinical study on duloxetine.

30) Administered a different study drug either currently or within 30 days before Visit 1.

31) Participation judged by the principal investigator or sub-investigator to be inappropriate for any other reason.

4.4 Screening dropouts

Patients who give informed consent to participate in the study, but are not then allocated to groups are considered to be screening dropouts. The following are entered in these patients' case report forms (CRFs): date of obtaining legal representative's written, informed consent; date of obtaining the patient's written assent (if applicable); demographic factors; information about meeting inclusion criteria and violating exclusion criteria; dropout date; reasons for dropping out; and adverse events leading to dropping out and serious adverse events.

4.5 Withdrawal from study or discontinuation of administration

The principal investigator or sub-investigator will as far as possible encourage subjects to complete the study, but subjects can withdraw for any reason. The principal investigator or sub-investigator will notify the sponsor about all discontinuations. If one or more of the following is applicable, the principal investigator or sub-investigator will discontinue study drug administration to the subject, and then discontinue the study. Completion of the study means completion of administration and observation up to Visit 9, or up to Visit 10 in the case of subjects who do not transfer to the extended long-term treatment study [study no.: 1702A3632 (NCT03395353)].

- The principal investigator or sub-investigator judges discontinuation to be necessary due to one or more serious or intolerable adverse events.
- The principal investigator or sub-investigator judges that insufficient efficacy of the study drug has resulted in aggravation of the primary disease, making discontinuation necessary.
- Pregnancy of the subject.
- The subject or his/her legal representative expresses the wish to withdraw from the study.
- The ineligibility of the subject is revealed during the screening period.
- The ineligibility of the subject is revealed after initiation of study drug administration.
- Administration of duloxetine at a dose of 40 mg/day or higher is difficult at or after Visit 3.
- Change in hospitalization status is necessary between Visits 1 and 8.
- The subject is unable to visit hospital due to moving home, transferring to a different hospital, etc.
- Death of the subject.

- It is judged that management of abnormal hepatic function test results is necessary, as is withdrawal on the basis of the discontinuation criteria (Appendix 2).
- Discontinuation is judged by the principal investigator or sub-investigator to be necessary for any other reason.

If a subject is withdrawn, the principal investigator will promptly report the withdrawal to the sponsor, and will as far as possible perform the assessments and tests for discontinuation of the treatment period or tapering period. Subjects withdrawn during the treatment period will be transferred to the tapering period. In the case of subjects withdrawn during the tapering period, the assessments for the follow-up period will be performed. All subjects withdrawn because of adverse events will be followed up until one of the following: (i) recovery from the adverse event to the state pertaining before administration initiation; (ii) the investigator or sub-investigator judges that the symptoms have stabilized or become chronic; and (iii) it is not possible to maintain communications with the subject. In addition, the date of completion or discontinuation of the treatment period or tapering period (as applicable), and the reasons for discontinuation (if applicable), will be recorded in the CRF.

5. Study drug regimen

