5.2 Dosage and regimen

Subjects who are formally enrolled after confirmation of eligibility will be randomly allocated to the duloxetine and placebo groups in accordance with the allocation method stipulated in Section 5.4. The two groups are shown in Table 5-1. Oral administration of duloxetine or placebo will be initiated the day after the registration (Visit 2), with administration once daily after breakfast for 7 weeks, in a 6-week treatment period and a 1-week tapering period. Treatments by methods other than the study drug administration are detailed in Section 6. .

Table 5-1. Study drug regimen for each group

Treatment group	Treatment period			Tapering period	
	Week 1	Week 2	Weeks 3 - 6	Week 7	
				First 3 days	Latter 4 days
Duloxetine group	20 mg/day	40 mg/day	40 or 60 ^a mg/day	20 ^b or 40 ^c mg/day	20 mg/day
	One 20-mg LY248686 capsule and one placebo capsule	Two 20-mg LY248686 capsules	Two 20-mg LY248686 capsules or three 20-mg LY248686 capsules	One 20-mg LY248686 capsule or two 20-mg LY248686 capsules	One 20-mg LY248686 capsule
Placebo group	0 mg/day	0 mg/day	0 mg/day	0 mg/day	0 mg/day
	Two 20-mg placebo capsules	Two 20-mg placebo capsule	Two 20-mg placebo capsules or Three 20-mg placebo capsules	One 20-mg placebo capsules or Two 20-mg placebo capsules	One 20-mg placebo capsules

When the dose is to be increased from 20 to 40 mg/day, or from 40 to 60 mg/day for the first time, the pre-increase dose must be administered for at least 7 days.

- When the CGI-S score is ≥ 3 , and there are no concerns about safety. If there are safety-related problems, as judged by the principal investigator, the dose can be reduced to 40 mg/day. If the CGI-S score is ≥ 3 , and there are no safety-related problems, after confirming the subject's clinical condition and safety, the dose can be increased again.
- If the duloxetine dose at discontinuation or completion of the treatment period was 40 mg/day.
- If the duloxetine dose at discontinuation or completion of the treatment period was 60 mg/day.

One of the following measures will be taken if administration is discontinued during the treatment period:

- 1) Discontinuation during week 1 of treatment period: Promptly discontinue administration.
- 2) Discontinuation during week 2 of treatment period: Discontinue after administration of the study drug at 20 mg/day for a tapering period of 7 days.

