- 3) Discontinuation during week 3 to 6 of treatment period: If the duloxetine dose at administration discontinuation is 60 mg/day, discontinue after tapering-period administration of the study drug, at 40 mg/day for 3 days, and 20 mg/day for 4 days.

If the duloxetine dose at administration discontinuation is 40 mg/day, discontinue after tapering-period administration of the study drug at 20 mg/day for 7 days.

However, tapered administration may be omitted if serious adverse drug reactions occur, there are safety-related problems, or the subject or his/her legal representative refuses the tapered administration.

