7.6.7.10 Pregnancy

The principal investigator or sub-investigator will instruct female subjects that, if they become pregnant during the study, they must stop taking the study drug, and immediately inform the principal investigator or sub-investigator. If a subject is found to be pregnant, the principal investigator or sub-investigator will withdraw her from the study. Information about the pregnancy will be reported to the sponsor as detailed below.

For all pregnancies that occur between initiation of study drug administration and completion of the follow-up period, the principal investigator will send a pregnancy follow-up report to the sponsor by fax or email within 24 hours after the pregnancy comes to light. Pregnancy complications and terminations for medical reasons will be reported appropriately, as adverse events or serious adverse events. Miscarriages will be reported as serious adverse events. In addition, pregnancies will be followed, and pregnancy follow-up reports will be submitted to the sponsor by fax or email. Even after completion of the follow-up period, if a pregnancy comes to light within 1 month after the final study drug administration, the study site will report it to the sponsor. At completion of pregnancy, by birth, miscarriage or termination, the outcome will be reported to the sponsor.

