Appendix 2: Management of abnormal hepatic function test results, and discontinuation criteria

In order to ensure subjects' safety, as well as to evaluate the causes of any hepatic dysfunction found, management on the basis of abnormal hepatic function test results, and the discontinuation criteria, are defined, on the basis of the FDA's July 2009 guidance (Guidance for Industry Drug-Induced Liver Injury: Premarketing Clinical Evaluation).

(1) Hepatic dysfunction criteria

The principal investigator or sub-investigator confirms whether or not the subject's laboratory test results meet any of the following criteria:

- a. AST and/or ALT >5 times the upper limit of normal (ULN) .
- b. AST and/or ALT >3 times the upper limit of normal (ULN) , and total bilirubin >2 times the upper limit of normal (ULN) .
- c. AST and/or ALT >3 times the upper limit of normal (ULN) , and signs and/or symptoms consistent with hepatitis or hypersensitivity (e.g. fatigue, nausea, vomiting, right upper abdominal pain or tenderness, jaundice, fever, rash, eosinophil increase by more than 5%).

(2) Principal investigator's actions

If one or more of the above hepatic dysfunction criteria is met, the principal investigator or sub-investigator will act as follows:

- Immediately ensure that the subject stops taking the study drug.
- If possible, have the subject visit hospital within 72 hours after the abnormalities are first found, to repeat the hepatic function tests for a supplementary evaluation of hepatic function.
- Until the hepatic function test result (ALT, AST, ALP, and total bilirubin) abnormalities cease, stabilize, or return to within the reference range or to the baseline, the subject's progression is observed two to three times per week, if possible.
- Report to the sponsor using the hepatic dysfunction follow-up assessment form, within 72 hours after the relevant abnormalities coming to the principal investigator's attention.
- Look into the option of consulting a hepatologist or other specialist.
- Look into the option of performing hepatic imaging, such as ultrasonography, magnetic resonance imaging, or computed tomography.
- Report all events that meet criterion b (above) as serious adverse events.

(3) Follow-up assessment

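### Protocol 4.5 sends all treatment-period withdrawals to the tapering period, contradicting 3.1 and 5.2 for week 1 and conflicting with the required stops for hepatic criteria and pregnancy

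*Protocol*

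**What the plan says.** Protocol 4.5 lists the reasons for which study drug is discontinued. Two of them are "Pregnancy of the subject" and the case where hepatic management is judged necessary, "as is withdrawal on the basis of the discontinuation criteria (Appendix 2"). After the list it says: "Subjects withdrawn during the treatment period will be transferred to the tapering period". The sentence carries no exception and no reference to 5.2, 7.6.7.10 or the stopping action in Appendix 2.

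Other parts of the protocol say:

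- Section 3.1 sets the tapering period for "subjects who complete the treatment period, or who withdraw from it during the second week or later". It describes double-blind dosing during that week and points to 5.2 for the method.
- Section 5.2: "Discontinuation during week 1 of treatment period: Promptly discontinue administration". For later weeks it describes a taper, then adds that "tapered administration may be omitted if serious adverse drug reactions occur", and extends this to safety-related problems and to refusal by the subject or legal representative.
- Appendix 2, for a subject who meets any of its hepatic criteria: "Immediately ensure that the subject stops taking the study drug".
- Section 7.6.7.10, on subjects who become pregnant: "they must stop taking the study drug".
- Appendix 1 marks study drug in the treatment-discontinuation column, with a footnote identifying it as the prescription for the tapering period and no exception.

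SAP 7.1 (tapering disposition) and SAP 10.1 item 6 (tapering-period adverse events) are both built on the subjects transferred to tapering. Neither defines transfer by dosing.

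**The concern.** In 3.1 the tapering period is a dosing period. An investigator who opens 4.5, the section that governs withdrawal, finds an instruction that leads to further study drug for every treatment-period withdrawal. Elsewhere the protocol says that some of these same subjects take no more drug. The population is aged 9 to 17, and the disputed point is whether dosing continues after a safety stop.

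The secondary stake is statistical. If sites or data managers follow 4.5 when recording transfer, the two SAP tables take in subjects who received no tapering dose. If they follow 3.1 and 5.2, week-1 withdrawals stay out.

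**Working it through.** The plan gives no figure to reproduce on this point. The check sets the sections side by side by type of withdrawal.

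| Withdrawal in treatment period | Protocol 4.5 | Other sections | Result |
|---|---|---|---|
| Week 1, any reason | Transfer | 3.1 sets no tapering period; 5.2 stops promptly | Direct contradiction |
| Week 2 or later, hepatic criterion | Transfer | Appendix 2 requires an immediate stop; 5.2 allows the taper to be left out for safety-related problems | Mandatory transfer against mandatory stop, with an optional exception between them |
| Week 2 or later, pregnancy | Transfer | 7.6.7.10 requires a stop; 5.2 does not name pregnancy | Mandatory transfer against mandatory stop |
| Week 2 or later, other safety problem or refusal | Transfer | 5.2 allows the taper to be left out | Rule plus an uncited exception; not counted as a conflict |
| Week 2 or later, all other reasons | Transfer | 3.1 and 5.2 also taper | Agreement |

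**Does a no-dose reading of transfer remove the conflict?** One could take transfer to mean attending the tapering-period visit without taking drug. That might serve for hepatic and pregnancy cases. It does not serve for week 1, because 3.1 sets no tapering period at all for those subjects.

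**Number affected.** Inputs are the target of 148 and the assumed 10% dropout, both from Protocol 8.2.

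- Assumed dropouts: 0.10 × 148 = 14.8, about 15.
- Only the first three rows of the table are in conflict. The documents give no split of dropouts by week or reason, so the number in conflict is an unknown part of these 15.

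**Effect on the SAP tables.** Let *n* be the subjects in an arm who took a tapering dose, *m* those counted as transferred without one, and *x* the subjects with a tapering-period event, held fixed. The reported rate is *x*/(*n* + *m*) instead of *x*/*n*, so it is multiplied by *n*/(*n* + *m*).

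As a ceiling, assume that dropout is as planned and splits equally between arms, that every dropout occurs in the treatment period without a tapering dose, and that everyone else tapers. Then *m* = 7.4 and *n* = 74 − 7.4 = 66.6 per arm, and the factor is 66.6/74 = 0.90. The rate would be understated by at most 10% in relative terms. The true factor lies between 0.90 and 1 under these assumptions and cannot be placed more exactly.

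**The case against.** The best defence is that the protocol already contains the governing rule. Section 3.1 limits who tapers and sends the reader to 5.2, which gives the week-by-week method and the exceptions. The safety-related limb of the 5.2 exception naturally covers a hepatic criterion and arguably pregnancy, so 5.2 allows what Appendix 2 requires. Section 3.1 also provides a one-week run-out for withdrawals with no tapering administration. Section 4.5 itself says that study drug is discontinued for the listed reasons, and it cites Appendix 2. On this view 4.5 lacks only a cross-reference.

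Much of this stands, and it lowers the practical risk. It does not remove the conflict:

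- A permission to leave out the taper does not reconcile a mandatory transfer with a mandatory stop.
- Section 4.5 cites Appendix 2 as a ground for withdrawal, then gives the transfer instruction without exempting that ground.
- The statement in 4.5 that drug is discontinued does not settle the matter, because 5.2 treats a taper as part of discontinuing from week 2 on.
- For week 1, nothing in 4.5 yields to 3.1 or 5.2.

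A reader might also infer that the protocol as a whole requires continued dosing in a child who meets a hepatic criterion. The documents do not support that: it follows only if the 4.5 sentence is read alone. Nor does 7.6.7.10 demand an immediate stop in pregnancy. Its wording is that the subject must stop; the word for immediacy there governs informing the investigator.

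**Conclusion.** The concern holds as an inconsistency between stated rules on a safety point. The week-1 contradiction is plain and rests on two sections. The hepatic and pregnancy conflicts are real on the text and are softened by the optional exception in 5.2.

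The number affected cannot be derived from the documents. A reader might take all of the roughly 15 assumed dropouts as falling under conflicting instructions. That is not supported: most withdrawals from week 2 on receive the same instruction in 3.1, 4.5 and 5.2, so 15 is the whole dropout allowance and not the affected group.

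The statistical effect is small. It touches the denominators of two descriptive summaries, in SAP 7.1 and 10.1 item 6. The primary analysis, its power and the overall adverse-event tables do not depend on who is counted as transferred. The 10% relative ceiling rests on the assumptions stated with it and is not an estimate. The point merits correction because of the safety ambiguity more than the table.

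**What to change.** **Protocol.** Reconcile 3.1, 4.5, 5.2, 7.6.7.10, Appendix 1 (the tapering prescription in the discontinuation column) and Appendix 2. Section 4.5 should refer to one rule that states which withdrawals enter the tapering period and which do not, by week and by reason. Which clinical rule applies is for the sponsor to decide.

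**SAP.** State in 7.1 and 10.1 item 6 whether transfer to tapering means having taken at least one tapering dose, and use the same definition in both.

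**Cost.** Wording only, with no change to design, sample size or the primary analysis. The protocol change would need IRB approval under 9.10. The SAP definition should need no new data, since 5.9 already has the start and end dates of each dose entered in the case report form. It should be settled before the key break, when the SAP is to be fixed.
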